1765 did. This will mostly happen if the A2 paramedic forgets to enrol the patient (and they are therefore not
1766 ‘consciously’ enrolled) or due to space issues they allow another paramedic to treat the patient. Note. If
1767 no advanced airway management was required once the enrolling paramedic arrived (e.g. because ROSC
1768 had already occurred) this is not a deviation.
- 1769 • The enrolling paramedic performed an alternative intervention to their allocation on their first advanced
1770 airway management attempt. According to the A2 protocol, enrolling paramedics should make two
1771 advanced airway management attempts with their allocated intervention before swapping to a different
1772 approach. The exception to this is solo responders in the intubation arm who are not allowed to intubate
1773 until another ambulance clinician arrives; occurrences of solo responders in the intubation arm using an i-
1774 gel before intubation will not count as a deviation but will count as a crossover in any per-protocol
1775 analyses (see section 6.2.2. for details).
- 1776 • The number of patients for whom the enrolling paramedic made only one attempt at their allocated
1777 intervention before swapping to an alternative advanced airway intervention will be noted. This is not
1778 considered a true protocol deviation as clinical reasons may have rendered a second attempt at the allocated
1779 intervention futile.

1780 The number of patients who were not ‘consciously’ enrolled in the trial will also be noted. This will often be
1781 the reason for deviations such as a patient receiving the wrong intervention, but is not a deviation in its own
1782 right.

1783 The frequency of each type of deviation will be tabulated by intervention allocation of the first A2 paramedic
1784 on scene (**Table T2 and Figure F6**). Note. It may be possible for patients to be classified as a protocol
1785 deviation for more than one reason.

1786 **3.6 Withdrawals**

1787 We have ethics approval to retain data collected up to the point of approach (after discharge from ICU) for all
1788 enrolled patients. However, patients who survive to ICU discharge and consent to participate in further data
1789 collection may later decide to withdraw. In some cases patients may be happy for data collection to continue,
1790 or for data collected up until withdrawal to be used, and therefore such patients will be included in the study

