- **Population 0:** The population of patients who were resuscitated but did not become trial patients (either because they were not attended by an A2 paramedic or were ineligible). Characteristics of this population will be compared to those in population 1 (see **Table 1**).

1821 The primary analysis will be performed on an ITT basis, with patients grouped by the allocation of their first
1822 A2 paramedic on scene (see section 6.2.2 for details).

1823 **3.8 Safety population**

1824 The safety population is all trial patients (cf. analysis population for the primary outcome). Only serious
1825 adverse events which are unexpected and related to the intervention are collected, so numbers are expected to
1826 be low. These will be presented along with all intervention details.

1827

1828 **4. DATA SOURCES**

1829 A number of variables collected in AIRWAY-2 are recorded in more than one place. The following table details
 1830 these variables and identifies the primary data sources and the order in which data will be selected; for example
 1831 gender will be taken from Form G2, if not available from Form G2 then Form G will be used, if not available
 1832 from Form G then Form E1 will be used and if not available from Form E1 then Form B will be used.

Variable	Data sources	Order of preference
Date and time of incident	Form A (CAD) Form E1 (paramedic)	Always use form A as this should be available for all patients
Gender	Form B (minimal dataset/CAD) Form E1 (paramedic) Form G (hospital details, only available for those surviving to hospital admission)	1. Form G2 2. Form G 3. Form E1 4. Form B
Date of birth (DOB)	Form B (minimal dataset/CAD) Form E1 (paramedic) Form G (hospital details, only available for those surviving to hospital admission)	1. Form G2 2. Form G 3. Form E1 4. Form B
Approximate age (Note. This variable will only be used if the date of birth is missing from all sources. If date of birth is recorded, age will be derived (see Section 5))	For patients who do not survive to hospital, age may be estimated on scene. If this is the case, this will be recorded on Form B (minimal dataset/CAD) Form E1 (paramedic)	1. Form E1 2. Form B
Presenting rhythm	Form B (minimal dataset/CAD) Form E1 (paramedic)	1. Form E1 2. Form B
Was event witnessed?	Form B (minimal dataset/CAD) Form E1 (paramedic)	1. Form E1 2. Form B
Who was the event witnessed by?	Form B (minimal dataset/CAD) Form E1 (paramedic)	1. Form E1 2. Form B

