1873 quartile range (IQR) if the distribution is skewed), and categorical data will be summarised as a number and
1874 percentage. The summary statistic headings given in **Tables T4** and **T5** are those we expect to use based on a-
1875 priori knowledge of the clinical measurements gained from previous studies. However, if distributional
1876 assumptions are not satisfied, changes will be made.

1877 Statistical tests to compare data not listed as outcomes will not be performed. Secondary outcomes 4
1878 (sequence of airway interventions delivered) and 7 (airway management in place when ROSC was achieved
1879 or resuscitation discontinued) will be described but not formally compared.

1880 **6.2 Primary and secondary outcome data**

1881 **6.2.1 Adjustment in models**

1882 The intention is to adjust the models for the three stratification (design) factors: ambulance trust (four levels),
1883 clinical experience (two levels) and the location of the paramedic’s base ambulance station (two levels) as
1884 fixed effects, and paramedic as a random effect (or a shared frailty term in the time to event model). For the
1885 mRS model where the majority of patients will have a poor outcome/death, the data may be insufficient to
1886 allow estimation of regression coefficients for all these variables. If this is the case, inestimable stratification
1887 variables will be dropped from the model and will be noted in a footnote. For the time to death model, if a cox
1888 model is used the analysis will be stratified by trust (to allow for varying baseline hazards) and adjusted for
1889 the other design factors. If either of the design factors do not meet the proportional hazards assumptions,
1890 stratification by these factors will also be implemented.

1891 **6.2.2 Data presentation and analysis models**

1892 For intention to treat analyses, data will be presented and analysed by the allocated group of the first A2
1893 paramedic on scene, regardless of what airway management the patient received. For per-protocol analyses
1894 (see sections 6.2.5 and 6.2.6), data will be presented and analysed by the allocation of the first advanced
1895 airway management used; if neither i-gel nor intubation was used (or if another SGA was used before an i-gel
1896 or intubation), the patients will be excluded from per-protocol analyses.

1897 All analyses and data presentation will be by intention to treat unless otherwise stated in the Table heading.

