1898 All outcomes listed in Sections 2.3 and 2.4 will be presented as per the template tables **Table T6** to **T8** and
1899 may also be presented graphically. General methods of presentation and assessing intervention effects are
1900 outlined below. For formal comparisons the intubation group will be the reference group. Details specific to
1901 each outcome are described as appropriate. Secondary outcomes 10 to 13 will not be reported in the primary
1902 outcome paper.

Date type	Outcomes
Binary	mRS (at discharge/30days) Initial ventilation success Regurgitation/aspiration Loss of previously established airway Return of spontaneous circulation (ROSC) 72h survival
Categorical	Actual sequence of airway interventions delivered ¹ Airway management in place when ROSC was achieved or resuscitation was discontinued or intervention from A2 paramedic stopped ¹
Continuous	Chest compression fraction

	Duration of ICU stay (presented separately for survivors and patients who die during ICU stay) ¹
	Duration of hospital stay (presented separately for survivors and patients who die during hospital stay) ¹
Time to event	Time from OHCA to when discharge/30 day mRS was assessed ^{1,3} Time to death ² Time to death (up to 72h)
Longitudinal	mRS (at discharge/30days, 3 months and 6 months) EQ-5D index score and visual analogue scale score (at discharge, 3 months and 6 months)

1903 *Note:-*

1904 ¹ These outcomes will be described but not formally compared

1905 ² Time to death will be formally compared in place of length of ICU and hospital stay

1906 ³ This is not a specified outcome but the DMSC raised it as a point of interest.

1907

1908 • **Binary outcomes** will be presented as numbers and percentages of patients in the category of interest.
1909 Outcomes will be compared between intervention groups using logistic regression. The intervention
1910 comparison estimate will be presented as an adjusted odds ratio (OR) with a 95% confidence interval
1911 (95% CI) and p-value. Formal statistical comparisons of treatment effects will only be performed if more
1912 than ten patients in total experience the outcome (with at least one event in each treatment group). .

1913 • **Categorical outcomes** will be presented as numbers and percentages of patients in each category.
1914 Outcomes will be compared between intervention groups using multinomial logistic regression.
1915 Treatment comparison estimates will be presented as adjusted odds ratios (OR) and 95% confidence

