1940 the best fit in terms of information criteria such as AIC, BIC and likelihood ratio tests will be used.

1941 **6.2.3 Statistical significance**

- 1942 For hypothesis tests two-tailed p-values < 0.05 are considered statistically significant.
- 1943 **6.2.4 Model assumptions**
- 1944 For all methods outlined underlying assumptions will be checked using standard methods, e.g. residual plots,
1945 tests for proportional hazards, etc. If assumptions are not valid then alternative methods of analysis will be
1946 sought. If outlying observations are found which mean models do not fit the data adequately, such
1947 observations will be excluded from the main analyses and comments made in footnotes.
- 1948 **6.2.5 Subgroup analyses**
- 1949 Two subgroup analyses for the primary outcome are specified in the protocol: Utstein comparator group vs
1950 non-comparator group and arrest witnessed by ambulance staff or not (**Figure F7**).
- 1951
- 1952 Due to concerns regarding ventilation success raised during the trial, a subgroup analysis of the primary
1953 outcome comparing patients whose i-gel or intubation airway management attempt(s) were or were not
1954 ‘successful’ during the first and/or second attempt (see section 5.2 for definition) will also be performed. This
1955 analysis will be performed per-protocol and as such will only include patients who received at least one
1956 advanced airway management attempt using an i-gel and/or intubation tube.
- 1957
- 1958 Subgroup effects will be fitted by adding a “sub-group x intervention” interaction term to the analysis model.
- 1959 **6.2.6 Sensitivity analyses**
- 1960 For the primary outcome, the following sensitivity analyses will be performed:
- 1961
 - ITT analysis including only patients who received at least one advanced airway management attempt
1962 using an i-gel and/or intubation tube.
 - Per-protocol analysis including only patients who received at least one advanced airway management
1963 attempt using an i-gel and/or intubation tube (see section 6.2.5 for additional sub-group analysis for
1964 this outcome).
 - ITT analysis including all patients who were attended by an AIRWAYS-2 paramedic but not
1965 resuscitated.
- 1966
- 1967
- 1968 **6.2.7 Missing data**
- 1969 In all tables missing data will be indicated by footnotes. If the amount of missing data differs substantially
1970 between treatment groups potential reasons will be explored.
- 1971 Missing predictors:

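### The analyses labelled 'per-protocol' group patients by the first advanced device used, so they are as-treated comparisons with no patient-level adjustment

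*Protocol*

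**What the plan says.** SAP 3.7 keeps the primary analysis on the randomised groups: "The primary analysis will be performed on an ITT basis, with patients grouped by the allocation of their first" A2 paramedic on scene.

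SAP 6.2.2 sets a different grouping for the per-protocol analyses: "data will be presented and analysed by the allocation of the first advanced" "airway management used; if neither i-gel nor intubation was used (or if another SGA was used before an i-gel" or a tube), the patient is excluded. Those are its only exclusions. Nothing there removes a patient who received the opposite trial device first.

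The word 'allocation' in that sentence could be misread as the randomised arm. SAP 3.5 settles it: for solo responders in the intubation arm, use of an i-"gel before intubation will not count as a deviation but will count as a crossover in any per-protocol" analysis. The patient stays in and changes group.

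The grouping is used twice for the primary outcome:
- SAP 6.2.6 lists a "Per-protocol analysis including only patients who received at least one advanced airway management" attempt with either trial device.
- SAP 6.2.5 says of the ventilation-success subgroup that the "analysis will be performed per-protocol and as such will only include patients who received at least one" such attempt.

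On adjustment, SAP 6.2.1 says "The intention is to adjust the models for the three stratification (design) factors: ambulance trust (four levels"), clinical experience and base location, with paramedic as a random effect. SAP 6.2.2 adds that for binary outcomes the "comparison estimate will be presented as an adjusted odds ratio (OR) with a 95% confidence interval".

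**The concern.** A per-protocol analysis ordinarily keeps patients in their allocated arm and leaves out those not treated as allocated. Here, patients whose first advanced device was the opposite one are transferred to the other group. The comparison is then between patients who received different devices, not between randomised groups.

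Ambulance clinicians are unblinded (Protocol 5.2.2). SAP 3.4 and 3.5 describe several routes to crossover: the wrong paramedic enrols, another paramedic takes over, the paramedic forgets or chooses not to follow the protocol, or a solo responder in the intubation arm uses an i-gel first. The last route exists in one arm only, so unequal crossover is plausible. The model's fixed effects describe paramedics, not patients, and cannot remove patient-level selection.

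A reader who sees 'per-protocol' beside the ITT result may take it as the effect under adherence. If crossovers differ in prognosis, it could appear to contradict a correct ITT result or to support a wrong one.

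**Working it through.** **The plan's own figure.** Protocol 4.7 gives 8% vs 10%, 5% significance, 90% power and 4,400 per group; SAP 6.2.3 makes tests two-sided. The standard two-proportion formula gives 4,301, or 4,401 with continuity correction, so 4,400 reproduces. With ICC 0.005 and 7 patients per paramedic, the design effect is 1 + (7 - 1) x 0.005 = 1.03, and 4,400 x 1.03 = 4,532 against the stated 4,535.

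**Inputs.** From the documents: N = 4,535 per arm and p = 9% good outcome. Assumed, because the documents give no values: cT, the share of the intubation arm receiving an i-gel first; cG, the share of the i-gel arm receiving a tube first; and rT and rG, the good-outcome rates in those crossovers. The nearest guide is overall adherence above 90% in the feasibility study (Protocol 2.1), which is not split by arm.

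**Formulas, with devices equivalent and 9% in each randomised arm (ITT difference zero).**
- i-gel-first rate = (p - cG x rG + cT x rT) / (1 - cG + cT)
- intubation-first rate = (p - cT x rT + cG x rG) / (1 - cT + cG)
- group sizes = N times each denominator; pooled two-sample z-test.

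**First scenario in full** (cT 10%, cG 0, rT 3%):
- i-gel first: (0.09 + 0.10 x 0.03) / 1.10 = 8.45%, n = 4,988.5
- intubation first: (0.09 - 0.10 x 0.03) / 0.90 = 9.67%, n = 4,081.5
- difference -1.21 points; SE = sqrt(0.09 x 0.91 x (1/4,988.5 + 1/4,081.5)) = 0.604 points; z = -2.01; p = 0.045 (0.048 with design effect 1.03).

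| cT | cG | rT | rG | i-gel first | Intubation first | Difference (points) | p (no design effect) |
|---|---|---|---|---|---|---|---|
| 10% | 0 | 3% | n/a | 8.45% | 9.67% | -1.21 | 0.045 |
| 10% | 2% | 3% | 3% | 8.56% | 9.52% | -0.97 | 0.11 |
| 15% | 2% | 3% | 3% | 8.31% | 9.90% | -1.59 | 0.009 |
| 10% | 2% | 5% | 5% | 8.70% | 9.35% | -0.64 | 0.29 |
| 10% | 5% | 13.5% | 9% | 9.43% | 8.53% | +0.90 | 0.13 |
| 10% | 10% | 4.5% | 4.5% | 9.00% | 9.00% | 0.00 | 1.00 |
| 10% | 2% | 9% | 9% | 9.00% | 9.00% | 0.00 | 1.00 |

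The fifth row shows that the sign reverses if crossovers do better than average. The last two rows show when the bias disappears.

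**Smaller analysis set.** SAP 6.2.5 and 6.2.6 restrict these analyses to patients with at least one i-gel or intubation attempt. With an assumed 4,000 per arm and design effect 1.03, the first scenario gives p = 0.063. If the rate in that set is also 7%, the difference is -0.81 points and p = 0.165.

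**Conventional per-protocol set.** Excluding the crossovers in the first scenario compares 9.00% with 9.67%, or -0.67 points. That is biased too, by a little over half as much as regrouping.

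**The case against.** The strongest defence is that nothing is hidden and nothing primary depends on this. The grouping rule is written out, and SAP 6.2.2 requires any analysis that is not ITT to be identified in its table heading. SAP 6.2.6 also places an ITT analysis restricted to patients with a trial-device attempt beside it. Table T2 and Figure F6 show deviations and devices received by allocation. All of this stands, and it limits the harm.

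Other parts of the defence also stand, against stronger readings that a reader might infer:
- *The comparison is unadjusted.* It is not: 6.2.1 adjusts for three design factors and paramedic. What is missing is any patient-level factor.
- *Every crossover is moved.* Patients with another SGA first are excluded, and those who switch after a first attempt with the allocated device stay in their group.
- *Crossovers are chosen on prognosis.* SAP 3.5 attributes some to miscommunication, lack of space or solo attendance, none of which is prognostic by definition.
- *The result is unbiased only if crossovers have average prognosis.* Equal selection in both directions also cancels.

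None of this makes the label right. A heading that says 'per-protocol' tells the reader that the analysis is not ITT, but not that opposite-device patients have changed group.

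**Conclusion.** The point holds as one of labelling and confounding, limited to one sensitivity analysis and one subgroup of the primary outcome. Both are as-treated by first advanced device and carry no patient-level prognostic adjustment. When crossover is both prognostic and unequal between arms, they can show a difference between equivalent devices: about -0.6 to -1.6 points in the first four scenarios, against the 2-point design difference, with p from about 0.29 to 0.009.

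The size rests on assumed crossover rates and prognosis, and on applying 4,535 per arm and 9% to a set that will be smaller and may have a different event rate. The documents fix neither the occurrence nor the direction of the bias. A reader might infer that the trial's main conclusion is at risk. The documents do not support that, because the primary analysis stays ITT and no decision rule uses these results. The change should be made, but it is not critical.

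**What to change.** In SAP 6.2.2, 6.2.5, 6.2.6 and the table headings:
1. Rename these analyses 'as-treated (by first advanced device)', and use the same term where SAP 3.5 refers to per-protocol analyses.
2. Add age, presenting rhythm, witness status and bystander CPR to their models. All four are listed in SAP section 4. State how missing values are handled, since 6.2.7 guarantees completeness only for the randomisation factors.
3. State that they are not a randomised comparison, and that patient-level adjustment reduces confounding without guaranteeing its removal.

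Optionally, add a complier-average estimate with allocated arm as instrument. It would need its assumptions stated, including exclusion, which is hard to defend with unblinded paramedics. It would also need a rule for coding patients with another SGA or no advanced airway, and its confidence interval would be wider. Offer it as an addition, not a required replacement.

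The cost of items 1 to 3 is SAP wording and a refit on data already collected. At the planned rate there are about 9,070 x 0.09 = 816 good outcomes before the restriction to attempted patients, so a few more covariates should be affordable.
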